7.2 PARTICIPANT DISCONTINUATION/WITHDRAWAL FROM THE STUDY

Participants (family caregivers and patients) are free to withdraw from participation in the study at any time upon request.

An investigator may discontinue a participant from the study for the following reasons:

- Lost-to-follow up; unable to contact subject (see **Section 7.3, Lost to Follow-Up**)
- Any event or medical condition or situation occurs such that continued collection of follow-up study data would not be in the best interest of the participant or might require an additional treatment that would confound the interpretation of the study
- The participant meets an exclusion criterion (either newly developed or not previously recognized) that precludes further study participation

The reason for participant discontinuation or withdrawal from the study will be recorded on the [specify] Case Report Form (CRF).

Clinical staff participants (nurses, social workers, chaplains, physicians, pharmacists) are also free to withdraw from the study at any time. Consenting clinical participants who are randomized but do not receive the study intervention may be replaced. Consenting participants who are randomized and receive the study intervention, and subsequently withdraw, or are discontinued from the study, will be replaced when possible.

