2.2 BACKGROUND

Polypharmacy for Home Hospice Patients is Burdensome, Harmful and Costly

Over 1.3 million Americans aged 65 years and older receive hospice services annually and 45% are cared for at home.⁵ These patients are prescribed an average of 10-12 medications daily^{6 7 8} and have progressively declining organ function that increases their risk of drug-related harm.⁹ Furthermore, many take questionably beneficial medications^{11 12 13} until death while simultaneously being prescribed an increasing number of end-of-life (EOL) symptom management drugs.⁸ This changing combination of medications contributes to stress and confusion for family caregivers (FCG) who are responsible who are responsible for patient medication management and administration.^{14 3}

Family (Informal) Caregivers Find Managing Complex Home Hospice Medication Regimens Stressful

Family (informal) caregivers are defined as “any relative, partner, friend or neighbor who has a significant personal relationship with, and provides a broad range of assistance for [an older person]”.⁴ Hospice is a particularly challenging setting for FCGs because they are responsible for complicated medication administration tasks that are *usually reserved for licensed healthcare professionals*.²⁸ An estimated 44 million adults, mostly women, provide this informal (i.e. unpaid) care.²⁹ They often feel inadequately prepared for this responsibility³⁰ and have fears about doing something wrong.^{28 30}

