7.1 DISCONTINUATION OF STUDY INTERVENTION/EXPERIMENTAL MANIPULATION

The study intervention, which targets hospice clinical staff, will be delivered one time at the beginning of the study and will be delivered to any new clinical staff joining the intervention site teams. We will inform the clinical sites of the end of the study when we 3 months after completion of study enrollment to allow for adequate, uncontaminated, collection of outcome data for all participants.

When a subject discontinues study procedures will be completed as indicated by the study protocol. If a clinically significant finding is identified (including, but not limited to changes from baseline) after enrollment, the investigator or qualified designee will determine if any change in participant management is needed. Any new clinically relevant finding will be reported as an adverse event (AE).

The data to be collected at the time of study intervention discontinuation will include the following:

- The reason(s) for discontinuing the participant from the intervention, and methods for determining the need to discontinue
- If the participant is due to complete assessments within 2 weeks of being discontinued from the study intervention, those assessments will be administered at the time of discontinuation; if the next scheduled assessments are more than 2 weeks from the discontinuation date, the discontinued participant will wait for the next scheduled assessment. Thereafter, the participant will be included in all future scheduled assessments, even though not participating in the intervention.

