8 STUDY ASSESSMENTS AND PROCEDURES

8.1 ENDPOINT AND OTHER NON-SAFETY ASSESSMENTS

The endpoint of the study is either patient death, disenrollment from hospice, or completion of 6 months of follow-up after study enrollment.

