8.2 SAFETY ASSESSMENTS

In accordance with applicable regulatory requirements and principles for the ethical conduct of research, a Safety Officer will be appointed by the NIA to oversee the safety of study participants.

Because the study population has, per the eligibility criteria, a limited expected prognosis of less than one year, death and the preceding associated development of symptoms related to the natural progression of disease are expected. Because the study setting is home hospice, hospitalizations related to the natural progression of disease are expected to be unusual. However, deaths, hospitalizations, and emergency department visits will be monitored.

Because the focus of the trial educational intervention focuses on medication-related management, review and support, medication changes and symptom changes potentially related to drug related problems (DRPs) will be monitored, including potential DRPs present upon study enrollment which, by definition, are not related to the research.

Medication changes will be identified by collecting medication lists every 2 weeks and iteratively identifying changes between lists. DRPs will be monitored by a trained research assistant who will screen the medical record using a Screening Algorithm of Potential Drug Related Problems at *study enrollment and every 2 weeks up to 2 months* for a retrospective chart review, and then monthly up to 6 months. These medical record will be reviewed for new clinical events, symptoms, abnormal lab events and drug levels, new reported drug allergies or drug associated problems identified by clinicians. Secondarily, a trained research assistant will also conduct a screening telephone interview with patients (or their caregiver, if patient is unable to participate) for potential DRPs using a method by Chrischilles³¹ *at 2 weeks and monthly* thereafter.

To ensure that potential DRPs, emergency department visits, hospitalizations and deaths are indeed unrelated to the research, these will be closely monitored by the study's Event Classification Pharmacist (ECP) comprised of a pharmacist using a procedure described below in Section 8.3.

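### Section 7.2 lets an investigator end a participant's follow-up because of an undefined confounding treatment, in a trial whose outcomes include medication changes, symptoms and drug-related problems

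*Combined protocol and SAP*

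**What the plan says.** Section 7.2 opens its list of grounds with "An investigator may discontinue a participant from the study for the following reasons". The second bullet has two limbs. One is that further data collection would not serve the participant's best interest. The other is that an event, condition or situation "might require an additional treatment that would confound the interpretation of the study". The reason for each removal is to be recorded on a case report form. Participants here are patients and caregivers: "Participants (family caregivers and patients) are free to withdraw from participation in the study at any time upon request".

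Four other places bear on this ground.

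- Section 7.1, on stopping the intervention only: "Thereafter, the participant will be included in all future scheduled assessments, even though not participating in the intervention".
- Section 8.1, on the end of follow-up: "The endpoint of the study is either patient death, disenrollment from hospice, or completion of 6 months of follow-up after study enrollment".
- Section 2.2, on many of these patients: "simultaneously being prescribed an increasing number of end-of-life (EOL) symptom management drugs".
- Section 8.2: "death and the preceding associated development of symptoms related to the natural progression of disease are expected".

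Sections 6.5 (Concomitant Therapy) and 6.5.1 (Rescue Therapy) are headings without text. Section 9.3 says that caregiver and patient outcomes are analysed separately. It gives no rule for analysing everyone enrolled, or for participants removed under 7.2.

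**The concern.** In a drug trial, a clause like this is usually aimed at a prohibited concomitant medication. Here nothing is prohibited. The intervention is training for hospice staff, and a patient's or caregiver's part is limited to record access and telephone questionnaires. A new treatment is therefore something the trial sets out to observe. The Synopsis and Section 3 list medication changes, regimen complexity, ESAS symptoms and drug-related problems or adverse drug withdrawal events among the endpoints.

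Removing someone because a treatment might be needed conditions follow-up on a post-allocation event that is tied to those endpoints. Three features make this matter.

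- The trigger is anticipatory and undefined, so two investigators could apply it differently.
- Section 6.3 states blinding for the coordinator who collects outcomes and for the adjudication team, but not for the investigator who applies 7.2.
- Section 2.3.1 names adverse drug withdrawal events as a risk of deprescribing. Treatment of such an event could fit the clause, so use of the clause could differ by arm, and drug-related-problem follow-up would stop where it is most informative.

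At stake are caregiver completion, the safety record, and the preliminary effect size that Section 9.4.3 wants for a larger trial.

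**Working it through.** **1. The plan's own figure.** Section 4.1: 2 agencies × 2 offices × 15 dyads = 60, or 30 per arm. This reproduces the stated target. The plan gives no removal rate, SD, effect size or power, so everything below on size is illustrative.

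**2. What the clause ends.** Section 7.1 covers stopping the intervention and keeps assessments going. Section 7.2 covers leaving the study, and the bullet's other limb is framed around continued collection of follow-up data. Section 8.1 lists three ends of follow-up, and removal by an investigator is not one of them. The three sections can be read together, but none says whether outcome or chart data are still collected after a 7.2 removal.

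**3. Effect on completion (Section 4.4).**

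| Participant | Needed to count as complete | If removed after week 2 |
|---|---|---|
| Patient | Baseline and 2-week assessments | Still a completer |
| Caregiver | Baseline, 2-week, and post-death (or 6-month) assessments | Non-completer, if the last assessment is not done |

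The completion loss therefore falls mainly on caregivers. One caregiver removed is 1/15 = 6.7 percentage points of an office, 1/30 = 3.3 points of an arm and 1/60 = 1.7 points of the trial. If 5%, 10% or 20% of 60 were removed (assumed rates), 57, 54 or 48 would remain.

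**4. Upper bound on bias in a continuous outcome.** Assume a standard normal outcome with higher scores worse, no true effect, removal of the worst-scoring fraction q in one arm only, and loss of all data from those removed. The mean of those who remain is −φ(z)/(1 − q), where z is the upper-q normal quantile.

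| q | z | φ(z) | Shift in mean (SD) |
|---|---|---|---|
| 0.05 | 1.645 | 0.1031 | −0.1031/0.95 = −0.11 |
| 0.10 | 1.282 | 0.1755 | −0.1755/0.90 = −0.195 |
| 0.20 | 0.842 | 0.2800 | −0.2800/0.80 = −0.35 |

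A simulation of an arm of 30 (200,000 replicates), dropping the 1, 3 or 6 worst scores, gave shifts of −0.07, −0.19 and −0.34 SD. The finite-sample result agrees with the formula: 3 and 6 of 30 are 10% and 20%.

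**5. How the planned analysis changes this.** Section 9.4.3 uses mixed models with repeated measures and adds covariates associated with missingness, under missing at random. No section says that data collected before removal are discarded, so earlier visits would still contribute and the shift should be smaller than in step 4. The protection is incomplete. The covariate examples are admitting diagnosis and race, and an investigator's judgement about treatment still to come may rest on deterioration that no earlier assessment captured.

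**The case against.** The strongest reply is that the authors cannot have meant routine symptom drugs. They expect symptoms to develop, collect medication lists every 2 weeks, and tabulate medication changes for each patient (Sections 8.2 and 9.4.6). The clause is permissive, and the recorded reason lets such removals be reported separately. Feasibility is analysed descriptively, and Section 9.2 says that the trial lacks power for efficacy. All of this stands and limits the consequences. It does not define the ground or restore follow-up once it has ended.

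A reader might also infer four stronger things that the documents do not support.

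- **That nearly every patient would meet the trigger.** Section 2.2 speaks of many patients and gives no rate. No section says that routine symptom drugs count as confounding. That they could is an inference from the missing definition.
- **That whole dyads are removed.** The clause names a participant, outcomes are analysed separately for patients and caregivers, and nothing says that removing one removes the other.
- **That 7.2 contradicts 7.1.** Section 7.1 governs stopping the intervention and 7.2 governs leaving the study. This is a tension in approach. Section 7.1 is also silent on analysis by arm.
- **That 0.1 to 0.35 SD is the likely bias.** The removal rates have no source in the documents, and the calculation ignores retained visits.

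It is also fair to say that the best-interest limb is discretionary too, so deleting the other limb does not remove all investigator judgement. That limb does, however, serve to protect the participant. The confounding limb does not.

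**Conclusion.** The point holds as a defect in a stated rule, and it should be corrected. An investigator not stated to be blinded may end follow-up on an undefined treatment ground, in a trial where added treatment is expected for many patients and is itself outcome data. Section 9.3 has no all-enrolled rule to offset the resulting selection.

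How often the ground would be used is unknown. The practical loss is greatest for caregiver completion, drug-related-problem follow-up and the preliminary effect estimates. Patient completion is protected once the 2-week assessment is done. The 0.1 to 0.35 SD range rests on one-sided removal of the worst scorers with complete loss of their data, and is an upper illustration only. In a pilot that disclaims efficacy power, this is an inexpensive correction worth making. It is not a threat to the trial as a whole.

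**What to change.** 1. In Section 7.2, second bullet, delete the limb "might require an additional treatment that would confound the interpretation of the study" together with the connecting word before it. Keep the best-interest limb.
2. Add to Section 7.2 that any added treatment is recorded as outcome data and that the participant stays in follow-up to the endpoints in Section 8.1. This matches the continued-assessment approach that Section 7.1 takes when only the intervention is stopped.
3. Add to Section 9.3 that all enrolled patients and caregivers are analysed by the allocation of their office, including data collected before any removal on the grounds that remain.

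The cost is a short protocol amendment. Medication lists and drug-related-problem screens are already scheduled, so no new data items or participants are needed. The change concerns data collection and analysis only and leaves clinical care as it is.

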7.3 LOST TO FOLLOW-UP

A participant will be considered lost to follow-up if study staff are unable to contact the participant after at least 3 attempts.

The following actions must be taken if a participant fails complete study assessments:

- The site will attempt to contact the participant and ascertain if the participant wishes to and/or should continue in the study
- Before a participant is deemed lost to follow-up, the investigator or designee will make every effort to regain contact with the participant (where possible, 3 telephone calls and, if necessary, a certified letter to the participant's last known mailing address or local equivalent methods). These contact attempts will be documented in the participant's medical record or study file.
- Should the participant continue to be unreachable, he or she will be considered to have withdrawn from the study with a primary reason of lost to follow-up

8 STUDY ASSESSMENTS AND PROCEDURES

8.1 ENDPOINT AND OTHER NON-SAFETY ASSESSMENTS

The endpoint of the study is either patient death, disenrollment from hospice, or completion of 6 months of follow-up after study enrollment.

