| | 
• Family caregiver medication burden, as measured by the Family Caregiver Medication Administration Hassle Scale.• Family caregiver satisfaction with care, as determined by likelihood to recommend• Polypharmacy• Potentially inappropriate medication use, as determined by a modified Medication Appropriateness Index• Medication regimen complexity, as measured by the Medication Regimen Complexity Scale• Medication changes• Adverse drug withdrawal events, as measured by a single item single item measure of change in medication since last visit and associated symptom change• Patient Quality of life (QOL), as measured by the McGill QOL Questionnaire (MQOLQ)• Patient Symptoms, as measured by the Edmonton Symptom Assessment System (ESAS)• Performance status, as measured by the Karnofsky Performance Status sale (KPS)• Unanticipated Events (whether study-related or not), as measured by time to first important event, consisting of:
○ admission to a hospital for any reason○ admission to an emergency department for any reason |

- Overall survival, as measured by time-to-death

Endpoints*:

Primary Endpoint: Trial completion

Secondary Endpoints: As described in Secondary Objectives

Study Population:

Eligible participants are adults aged 65 years and older with advanced life-limiting illness with an estimated prognosis of 1-6 months who are prescribed 5 or more medications and their family caregivers.

Phase* or Stage:

Feasibility Trial

**Description of Sites/Facilities
Enrolling Participants:**

Hospice Sites. EOL practices vary regionally.¹³⁻¹⁵ Thus, we are partnering with two large, geographically distinct home hospice agencies to begin exploring the generalizability of SPECTORx nationally. Each agency has multiple offices serving different

local regions within their states. Care Dimensions (Massachusetts) has 2 offices serving 4 counties in Eastern MA, and CNS Home Health & Hospice (Utah) has 10 offices throughout Utah.

Description of Study Intervention/Experimental Manipulation:

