The study intervention is a patient-centered medication review and FCG support program called “Standardized PatiEnt-CenTered medicatiOn Review (SPECTORx) in Home Hospice”. This intervention combines 3 innovative, complementary, educational programs that, together, train hospice staff to create a comprehensive, patient-centered, medication management plan. These evidence-based tools equip hospice staff: 1. to systematically identify medications that can be stopped or tapered using STOPPFrail (Screening Tool of Older Persons Prescriptions) criteria; 2. to discontinue medications appropriately; and 3. to educate and support FCGs with medication administration and management challenges. The SPECTORx program also creates an online learning community for hospice clinicians to promote ongoing education and practice change.

[figure not shown]
Study Duration*:

Estimated study duration from earliest enrollment to completion of data collection is 12 months.

Participant Duration:

Estimated time it will take for each individual participant to complete all study-related tasks (i.e. time from enrollment to patient death, discharge from hospice, or end of study) is 6 months.

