1.2 SCHEMA

1.3 SCHEDULE OF ACTIVITIES

| STUDY PERIOD | | | | | |
|--|---|---------|---------|------------------------|----------------------|
| TIMEPOINT | Screening / Post-allocation Enrollment | | | Close-out | |
| | 2 weeks | 4 weeks | 6 weeks | 8 weeks and monthly | 24 weeks or death |
| ENROLLMENT | | | | | |
| Eligibility screening | x | | | | |
| Informed consent | x | | | | |
| FEASIBILITY | | | | | |
| SPECTORx Intervention | | | | | |
| Attention Control | | | | | |
| ASSESSMENTS (Source/Items) | | | | | |
| FCG/Demographics | x | | | | |
| FCG/Family Caregiver | x | x | x | x | x |
| Medication Administration | | | | | |
| Hassle Scale | | | | | |
| FCG/Potential medication related symptom change | | x | x | x | x |
| FCG/Patient Centered Medication Communication | x | x | x | x | x |
| FCG/Satisfaction with Care (Likelihood to recommend) | | | | | x |
| EMR/ PT Demographics | x | | | | |
| EMR/ PT Primary Hospice Admitting Diagnosis* | x | | | | |
| EMR/ PT Comorbid Illness* | x | | | | |
| EMR/PT Medications* | x | x | x | x | x |
| EMR/PT KPS* | x | x | x | x | x |
| EMR/PT Survival* | | x | x | x | x |
| EMR/PT Health resource utilization (hospital admissions, emergency department visits)* | | x | x | | x |

| | | | | | |
|---|---|---|---|---------------------------|---|
| EMR/Potential Drug Related Problem Screen | x | x | x | x | x |
| Patient/Potential Drug Related Problem | | x | | x (& monthly thereafter) | |
| Patient/MQOLQ | x | x | x | x | x |
| Patient/ESAS | x | x | x | x | x |

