2.3 RISK/BENEFIT ASSESSMENT

2.3.1 KNOWN POTENTIAL RISKS

The risks and costs vs benefits of reducing polypharmacy for patients with advanced disease and their family caregivers remains a genuine clinical uncertainty. Multiple studies support the use of myriad individual chronic disease medications, such as statins, in elderly adults with appropriate indication. However, the benefit of continuing chronic disease medications after hospice admission on quality of life, family caregiver medication hassle, or patient survival is unknown. Simplifying medication regimens through a process of deprescribing is one remedy to medication complexity as death approaches, but may be associated with potential risk of stress to family caregivers about making decisions regarding stopping medications and additional potential risk of adverse drug withdrawal events after stopping medications - a particular concern when abruptly stopping medications with long half lives that are known to require tapering protocols.

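### Sections 8.1 and 1.1 end follow-up when a patient leaves hospice alive, so later hospital/ED use and deaths are not captured; this conflicts with 1.3 and 4.4

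*Combined protocol and SAP*

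**What the plan says.** **End of follow-up.** Section 8.1: "The endpoint of the study is either patient death, disenrollment from hospice, or completion of 6 months of follow-up after study enrollment". The synopsis (1.1, Participant Duration) describes participation as "time from enrollment to patient death, discharge from hospice, or end of study". Both stop at departure from hospice.

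**Endpoints.** The synopsis lists among the secondary outcomes "Unanticipated Events (whether study-related or not), as measured by time to first important event". Its components are "admission to a hospital for any reason" and ED admission on the same all-cause basis. It also lists "Overall survival, as measured by time-to-death".

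**Source.** The Schedule of Activities (1.3) has the rows "EMR/PT Health resource utilization (hospital admissions, emergency department visits" and "EMR/PT Survival". Each carries the EMR label, and no other source is listed for either item.

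**Text that points the other way.** The last column of 1.3 is a close-out at 24 weeks or death, and both rows are marked there. Section 4.4 has the caregiver complete an assessment after the death, or at 6 months if the patient is still alive. Neither mentions leaving hospice as an end.

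**Analysis.** Section 9.4.3 gives mixed models for continuous outcomes and covariate adjustment for missing data under missing at random. The plan contains no time-to-event method, no censoring rule, and no statement on how death or live discharge is handled.

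**The concern.** Departure from hospice is not obviously unrelated to the outcomes. A family may leave because it wants hospital care. It may also leave because it is troubled by changes to the medications: section 2.3.1 names a "potential risk of stress to family caregivers about making decisions regarding stopping medications", although it does not say that families would leave hospice because of it. If follow-up ends at departure, what happens next falls outside the data for exactly these patients.

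Three uses of the data are affected. Survival and health resource utilization go to the Safety Officer and the NIA Project Officer (8.3.1), and the Safety Officer's three-monthly review informs whether the trial continues (10.1.6). Section 9.4.3 intends the pilot to supply a preliminary effect size for a larger trial, so a difference between arms in who leaves could be carried forward as a difference in outcome. For overall survival, a live discharge would end observation at a moment that may be related to prognosis.

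**Working it through.** **1. The rules side by side.**

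| Place | What ends follow-up | Does leaving hospice alive end it? |
|---|---|---|
| 8.1 | death, leaving hospice, or 6 months | yes |
| 1.1, Participant Duration | death, discharge, or end of study | yes |
| 1.3, close-out column | 24 weeks or death | not mentioned |
| 4.4 | caregiver assessment after death or at 6 months | not mentioned |
| 7.1 | assessments go on after the intervention is discontinued | not mentioned |

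The first two cannot be followed together with 1.3 and 4.4 for a patient discharged alive in, say, week 5. Section 7.1 shows that the authors were willing to go on assessing people, but it concerns stopping the intervention.

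**2. Which events are lost under 8.1.**

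- Admission before discharge: within follow-up, and can be counted.
- Admission that triggers discharge: may be in the record. Whether it counts is not stated.
- Admission after discharge: outside follow-up.
- Death after discharge: outside follow-up.

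**3. Other sources.** Section 8.2 says that deaths, hospitalizations and ED visits will be monitored, but names no second source and no window after discharge. Its telephone interview screens for potential drug-related problems.

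**4. Size.** The plan states no figure to reproduce here beyond the sample: 2 agencies × 2 offices × 15 = 60 dyads, or 30 per arm. It gives no hospital/ED rate, survival figure or disenrollment rate. The next lines are arithmetic on assumed values, not an estimate.

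Let p be the true share of patients with a hospital/ED event and m the share of those events lost because the patient had left. Expected recorded events per arm = 30 × p × (1 − m).

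| Assumed p | True events per arm | Recorded, m = 20% | Recorded, m = 60% |
|---|---|---|---|
| 10% | 3 | 2.4 | 1.2 |
| 20% | 6 | 4.8 | 2.4 |
| 30% | 9 | 7.2 | 3.6 |

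With equal m in both arms the ratio of events is unchanged and only the level is too low. With m = 20% in one arm and 60% in the other, the ratio is (1 − 0.2)/(1 − 0.6) = 2.0 with no true difference. With the arms reversed it is 0.5. The value of m could lie anywhere from 0 to 1.

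**5. Why the handling of death has to be written down.** Assume constant hazards. Let h = −ln(0.8)/24 per week, which is a 20% hospital/ED risk over 24 weeks if nobody died, and let d = ln 2/(median survival in weeks). One minus Kaplan-Meier with death as ordinary censoring gives 1 − exp(−24h) = 0.20. The cumulative incidence is h/(h + d) × (1 − exp(−24(h + d))):

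- median survival 6 weeks: 0.071
- 10 weeks: 0.100
- 16 weeks: 0.127

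The plan names neither method. The same data would give quite different figures depending on a choice that is not made.

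**The case against.** The strongest reply is that the plan does not clearly stop follow-up at discharge. The close-out in 1.3 and the caregiver assessment in 4.4 suggest that it continues, and the sites may work that way. This stands in part: the documents conflict, and it would be wrong to report a single rule that certainly loses the events. But 8.1 is explicit and the synopsis agrees with it, so a site following the protocol could properly stop.

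A reader might go further than the text allows in four ways.

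- *That a patient who leaves for hospital care is necessarily censored by the event being counted.* No censoring rule is written, and an admission before or at discharge may be recorded. Loss is certain only for events after discharge.
- *That caregivers are never asked about hospital or ED use.* The questionnaires are not in the documents. What can be said is that 1.3 lists no caregiver source for it. Nor do the documents say whether the EMR is the hospice's record alone.
- *That a given percentage of events will be missed.* Such a figure would largely return whatever share was assumed to leave.
- *That a seemingly empty interim cell in the hospital/ED row of 1.3 is a gap.* Columns may have shifted in extraction. A chart review at close-out could also date earlier admissions.

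Other fair points are that differential departure by arm is a possibility and not a finding; that 8.2 expects hospitalizations from disease progression to be unusual; that the endpoint table in section 3 includes survival but not hospital/ED use; and that 7.1 and 7.2 already record reasons for discontinuation or withdrawal. Leaving death out of the hospital/ED outcome is a legitimate choice, since survival is a separate endpoint. None of these settles what happens after a live discharge.

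**Conclusion.** The concern holds in this form: 8.1 and the synopsis end follow-up at departure from hospice, in conflict with 1.3 and 4.4, while two secondary endpoints depend on events that can occur afterwards and have only the EMR as a listed source. Under the 8.1 rule, admissions and deaths after a live discharge are not captured. The loss may be informative, because leaving hospice may be related to hospital use, and it could differ by arm.

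The size cannot be estimated from the documents. The event counts and risks shown in the check rest on assumed rates and illustrate only how the loss and the treatment of death would act.

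These are secondary and safety outcomes in a 60-dyad feasibility pilot that disclaims power in 9.2. The primary feasibility objective is not invalidated, though whether the caregiver of a patient discharged alive can count as a completer under 4.4 depends on the same reconciliation. The change should be made, chiefly for the safety summary and for the effect estimates meant to plan the larger trial.

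**What to change.** 1. Amend 8.1 and the synopsis so that vital status and hospital/ED use are ascertained to death or 24 weeks whether or not the patient is still in hospice, and align 1.3, 4.4 and 7.1 with this.
2. Add hospital/ED questions to the caregiver calls already scheduled, and one contact at 24 weeks for families that left hospice. List the caregiver as a source in 1.3 beside the EMR, and say whose record the EMR is.
3. State that an admission leading to disenrollment counts as an event.
4. Record the date of and reason for disenrollment, and report both by arm.
5. In 9.4.3, summarise first hospital/ED event as cumulative incidence by arm with death as a competing event. State that discharge alone does not end observation for this outcome or for survival.

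Cost: a few added questions on existing calls, a few extra calls to families no longer in hospice, one sentence in the telephone consent script to cover that contact, and short changes to the protocol and analysis text. The downside is the added contact with families who have left hospice.
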